9.0 STATISTICAL PLAN

9.1 Sample Size Determination

The sample size for this study is logistically rather than statistically driven.

A total of 50 patients will be enrolled, randomized and successfully provided early cannulation within 72 hours, and followed to 6 months. Another group of 25 patients will be randomly assigned and provided cannulation for 10 or more days after implant and followed only to 30 days to assess perioperative MACE rates. No loss to follow-up is projected at 30-days post implantation.

Previously published patency data (refer to the background section above) will be used at 12 weeks and 6 months for clinical context. The early access study group results will be compared with these previously published data, which were reported for Artegraft normal cannulation times. It should be noted that complications may or may not result in an early access failure. Confidence intervals will be presented around each endpoint. The observed rates will be numerically compared with the expected rates and no formal statistical hypothesis will be tested.

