- Mahajan et al.²⁵also published an abstract describing initial results related to early access of Artegraft with the desire to minimize the time a patient would require the use of a tunneled hemodialysis catheter. In the period from November 2013 through October 2015 Mahajan implanted 58 patients with Artegraft. Of these 58 patients, 24 (41%) underwent early access, defined as access in less than 7 days. Seventeen (29%) of these patients had successful access on postoperative day 1, one underwent access on day 4, and six underwent access on day 7. Primary and secondary patency at 30 days was 90% and 96%, respectively. There was no early graft infection, thrombosis, or bleeding. He concluded that early access of the BCA graft is an alternative in patients with disadvantaged veins and in patients who require revisions of a native fistula due to bleeding and aneurysmal degeneration, thus eliminating the need for a temporary tunneled catheter in this patient population.
- Abdoli presented the work of his colleagues (Mahajan et al. ²⁶) on early Artegraft access at the 31st Western Vascular Society Meeting in 2016. In this study 36 grafts were subject to early access, defined as access within seven days. Twenty-one (58%) patients were cannulated within one day. At 180 days, primary patency was 44% and secondary patency was 80%. No difference was

Artegraft, Inc.
Protocol: ARTCT.BEACH.001

Version 4.0 CONFIDENTIAL

- observed in primary and secondary patency with grafts subjected to early or standard access time. Early access resulted in an overall complication rate of 17%, whereas standard cannulation resulted in an overall complication rate of 22%.

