4.0 OBJECTIVES AND ENDPOINTS

Table 6: Study Objectives and Endpoints

| able 0. Study Objectives and Endpoints | | | | |
|---|---|--|--|--|
| Study Objective | The objective of the BEACH Trial is to demonstrate that early access of Artegraft is associated with acceptable rates of successful early access, and acceptable rates of a composite of adverse events, to support a modification of existing device labeling stating that Artegraft is capable of cannulation within 72 hours post implantation. | | | |
| Primary Effectiveness Endpoint | Early access success, defined by three cannulations, the first one started within 72 hours post implantation, all with minimum dialysis flow rates of 250 ml/min pump flow rate, with a minimum 17-guage needle. | | | |
| | Expectations: $^{\sim}80\%$ of patients in the early access group will have first cannulation within 72 hours. | | | |
| | Expectations: ~90% of patients receiving early access will have 3 successful cannulations. | | | |
| Primary Safety Endpoint | A composite of major adverse clinical events (MACE) including perigraft infection, hemorrhage, thrombosis, steal syndrome, and pseudoaneurysm within 30 days after first cannulation [Day 0] in the early-access and late-access groups. | | | |
| | Expectation: ~20% of patients will have at least one MACE event; no significant difference in event number or type between early and late access groups. | | | |
| | All MACE will be adjudicated by an independent accessor. | | | |
| Secondary Effectiveness Endpoints | Patency (Primary, Assisted Primary, and Secondary) at 30 days after first successful cannulation [Day 0], and at 12 weeks and 6 months after implantation in the early-access group and at 30 days post-Day 0 in the lateaccess group. The late access group will also be assessed for patency at 6 months through a telephone interview or office visit to provide a more robust data set. | | | |
| | Expectations: | | | |
| | Patency rates [all 3 types] at 30 days will be similar in the early and late access groups. | | | |
| | We expect primary patency to be ≥85%, ≥75% and ≥65% at 30 days, 3 months, and 6 months, respectively. | | | |
| | Primary-assisted patency rates at 30 days, 3 months, and 6 months will be ≥85%. | | | |
| | Secondary patency rates will be ≥90% and ≥90% at 3 and 6 months, respectively. | | | |

Artegraft, Inc.
Protocol: ARTCT.BEACH.001

Version 4.0 CONFIDENTIAL 21June2019 Page 29 of 81

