6.8 Number of Patients Included in Clinical Investigation

A total of 50 patients will be enrolled, successfully provided early cannulation within 72 hours and followed to 6 months. This sample size is logistically rather than statistically driven. Patients randomized to the early access group not cannulated in the <72-hour period will still be followed for 30 days after first cannulation. It is estimated that up to 10 additional patients may fall into this category.

It is expected that 25 enrolled patients will have late access [>/= 10 days] of the Artegraft. These patients will be followed only to 30 days post Day 0 to assess perioperative MACE and patency rates. The late access group will also be assessed for patency at 6 months through a telephone interview or office visit to provide a more robust data set.

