9.2 Statistical Methods

9.2.1 Overview of Statistical Analysis

Descriptive statistics will be performed separately for the early and late access treatment groups. The estimated patency rates will be calculated using the SVS reporting standards guidelines.³¹ Should there be considerable site differences and with sufficient number of patients within sites, stratified and/or weighted estimates may be performed.

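### Six-month early-access patency is set beside published and expected rates, but no early-versus-late estimate is planned at that time, although the arms are randomised and late-arm patency is collected

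*Combined protocol and SAP*

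**What the plan says.** Section 9.1 states that published patency data "will be used at 12 weeks and 6 months for clinical context", and then: "The early access study group results will be compared with these previously published data, which were reported for Artegraft normal cannulation times". It continues: "The observed rates will be numerically compared with the expected rates and no formal statistical hypothesis will be tested". On size it says: "The sample size for this study is logistically rather than statistically driven".

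The expected rates are in the objectives and endpoints table of Section 4.0. Primary patency at 6 months is to be at least 65%. For secondary patency the table reads: "Secondary patency rates will be ≥90% and ≥90% at 3 and 6 months, respectively". The only between-arm patency expectation in that table is similarity at 30 days.

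Section 7.6 randomises 2:1, stratified by site. Section 6.8 adds: "The late access group will also be assessed for patency at 6 months through a telephone interview or office visit to provide a more robust" (sentence cut here). Sections 4.0, 5.1, 5.4, 6.7, 6.7.2 and 8.6 and the late-access schedule of assessments also include this contact. Section 9.1 itself, however, says the late group is followed only to 30 days, and Section 3.3 also gives only 30 days.

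On analysis, Section 9.2.1 says: "Descriptive statistics will be performed separately for the early and late access treatment groups". Section 9.2.3 plans Kaplan-Meier curves and optional Cox regression on baseline risk factors. Neither names a 6-month difference between arms.

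**The concern.** The objective is a label change on access timing. Whether early access costs graft patency is a question about early against late access in the same kind of patient. Randomisation within site answers that question; a comparison with past series answers whether these sites resemble those series.

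The protocol's own background shows how far series differ. Published 1-year primary patency runs from 28% to 73%. Section 3.2 cites an early-access series with 44% primary and 80% secondary patency at 180 days, in which no difference was "observed in primary and secondary patency with grafts subjected to early or standard access time". The 6-month row of the reported patency table has a primary minimum of 69%, so it does not reflect that series. Section 3.2 also remarks that the reviewed patency literature supports hardly any conclusions.

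If the enrolled case mix is poor, early access can look deficient when timing does nothing. If it is good, a loss could go unnoticed. The reader is given the external benchmark but no between-arm estimate with a stated population, time origin and interval.

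**Working it through.** **The plan's own figures.** The sample size has no alpha, power, effect or margin, so there is nothing to reproduce; 50:25 does match 2:1. The tabulated 6-month primary mean is consistent with its range: (69 + 73)/2 = 71.

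**Inputs.** Early n = 50 and late n = 25 (Section 9.1). Expected 6-month rates are 65% primary and 90% secondary (Section 4.0). Tabulated 6-month rates are 69% to 73% primary and 89% secondary (Section 3.2). The cited 180-day series gives 44% and 80% (Section 3.2).

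**Assumptions.** Complete 6-month data, patency treated as binomial, and no timing effect, so that both arms share the true rate p. The 44% and 80% are taken to apply to both access groups, as the reported lack of difference suggests.

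**External comparison.** Reaching 65% of 50 needs 33 patent grafts (32.5 rounded up); reaching 90% needs 45. The chance of a point estimate below the expectation is P(X ≤ 32) or P(X ≤ 44), with X ~ Binomial(50, p).

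| Endpoint | True p | P(below expectation) |
|---|---|---|
| Primary, 65% | 73% | 0.10 |
| Primary, 65% | 71% | 0.17 |
| Primary, 65% | 69% | 0.27 |
| Primary, 65% | 60% | 0.76 |
| Primary, 65% | 55% | 0.92 |
| Primary, 65% | 44% | 0.999 |
| Secondary, 90% | 89% | 0.48 |
| Secondary, 90% | 80% | 0.95 |

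The result moves from 0.10 to 0.999 with case mix alone. Part of the 0.48 arises because the 90% expectation lies above its tabulated source of 89%.

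**Randomised contrast.** Newcombe 95% interval for the difference, 50 against 25, enumerated over all outcomes. With no timing effect, the interval lies wholly below zero in 3.0% of trials at 44%, 2.9% at 55%, 2.2% at 71% and 2.0% at 80%. Unlike the external comparison, it hardly depends on the base rate.

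**Precision.** For 40/50 against 20/25 the Wilson limits are 0.670 to 0.888 and 0.609 to 0.911.
- Lower limit: 0 − √[(0.800 − 0.670)² + (0.911 − 0.800)²] = −0.171.
- Upper limit: 0 + √[(0.888 − 0.800)² + (0.800 − 0.609)²] = +0.210.

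The approximate half-width, 1.96 × √[p(1 − p)(1/50 + 1/25)], is 0.238 at 44%, 0.218 at 71%, 0.192 at 80% and 0.150 at 89%. Adding the up to 10 early-randomised patients who miss the 72-hour window (60 against 25) changes 0.192 only to 0.187.

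**The case against.** The strongest reply is that nothing is being judged. Section 9.1 calls the published data context and rules out a formal test, and patency is a secondary endpoint with stated expectations. That stands: there is no decision rule, and a point estimate below an expectation triggers nothing.

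A reader might infer that the late arm goes unused. The documents do not support that. The arms are to be described separately, Kaplan-Meier curves are planned, effectiveness is reported by randomised group (Section 9.2.8), and Section 9.1 promises confidence intervals around each endpoint. What is missing is the difference itself.

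A reader might also infer that the external comparison will show a shortfall almost every time when timing has no effect. That holds only near the 44% or 55% primary rates. At the tabulated 6-month rates the chance is 0.10 to 0.27.

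Nor do the documents show that a large loss would usually be hidden. An example with 91% late and 71% early primary patency meets 65% with probability 0.83, but 91% exceeds the table's maximum of 73% at 6 months. With 71% late and 51% early, the external comparison falls below 65% with probability 0.98, while the Newcombe interval excludes zero in only 0.40 of trials. The external figure does better there because the late arm happens to match the published mean, which cannot be known without looking at that arm.

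Two practical limits also stand. In the late-access schedule, documentation of graft interventions stops at Day 30 and there is no 12-week visit, so primary and assisted primary patency at 6 months are not well supported in that arm. And the 50 early patients are selected on successful cannulation within 72 hours; those who miss the window are replaced, so 50 against 25 is not strictly the randomised comparison.

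**Conclusion.** The point holds as a gap in the planned analysis. Section 9.1 gives 6-month early-access patency an external reference only, and no section plans the between-arm estimate that randomisation makes possible. The external comparison cannot separate timing from site, era and case mix: with no timing effect, the chance of falling below expectation ranges from 0.10 to 0.999 for primary patency and from 0.48 to 0.95 for secondary, over rates the protocol itself cites. These figures assume 50 complete early patients.

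The randomised contrast removes that dependence but is imprecise, at roughly ±15 to ±24 points for true rates of 89% down to 44%. It can serve as an estimate with an interval. It cannot confirm a difference reliably, and an interval that includes zero would not show that patency is similar.

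**What to change.** In Sections 9.1 and 9.2.3, add the early-minus-late difference in 6-month Kaplan-Meier secondary patency with its 95% CI.

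- **Population:** all patients by randomised group, including those randomised to early access but not cannulated within 72 hours.
- **Time origin:** implantation in both arms, as in the SVS definitions quoted in Section 3.2. Visits are scheduled from Day 0, which falls later after implant in the late arm.
- **Primary and assisted primary patency:** report the 6-month contrast only if dated interventions are captured for the late arm at the scheduled 6-month contact.
- **External rates:** keep published and expected rates as background.
- **Interpretation:** state that the interval is descriptive and is not evidence of equivalence.

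Reconcile Sections 9.1 and 3.3, which give the late arm 30 days only, with the sections that add the 6-month contact. Do the same for early-access drop-outs, who have 30-day follow-up in the protocol summary but a 6-month contact in their schedule of assessments.

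The cost for secondary patency is SAP wording and one table, with no new patients, and no new visits where the 6-month contact applies. Contrasts for the other two patency types would need extra data capture at that contact. The main downside is the wide interval, which limits what the trial can say about similar patency.

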1.0 PROTOCOL SUMMARY

| Clinical Investigation Title | BEACH Trial: Bovine Early Access, Compatibility, and Hemostasis Trial Study to Evaluate the Safety and Effectiveness of Early Access in Patients Who Require an Arteriovenous Conduit for Hemodialysis using the Artegraft [®] Collagen Vascular Graft [™] |
|---------------------------------|--|
| Short Title | Bovine Early Access, Compatibility, and Hemostasis (BEACH) Trial |
| Investigational Device | Artegraft® Collagen Vascular Graft™ (Artegraft) |
| Intended Use | The intended use and design of the Artegraft is unchanged. The following paragraph is from the Artegraft IFU: "The Artegraft is intended for use distal to the aorta as a segmental arterial replacement, as an arterial bypass, as an arteriovenous shunt where more conventional methods have proven inadequate, or as an arterial patch graft." |
| Study Objective | The objective of the BEACH Trial is to demonstrate that early access of Artegraft is associated with acceptable rates of successful early access, and acceptable rates of a composite of adverse events, to support a modification of existing device labeling stating that Artegraft is capable of cannulation within 72 hours post implantation. |
| Study Population | Patients with end-stage renal disease (ESRD) who require hemodialysis and are suitable for an arteriovenous graft (AVG) for hemodialysis. |
| Study Design | Prospective, multi-center randomized, open-label, treatment trial Eligible patients will be implanted with the Artegraft. After successful implant, Patients will be randomly assigned in a 2:1 ratio to early access [within 72 hours post implantation] or late access [>/= 10 days], of the Artegraft device. Day 0 is the date of first successful cannulation of the Artegraft for each patient. Patients with early access will be followed for 6 months post implantation. Patients with late access will be followed to at least 30 days after first access [30 days post Day 0]. The late access group will also be assessed for patency at 6 months through a telephone interview or office visit to provide a more robust data set. |

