9.2.2 Estimating primary effectiveness and primary safety endpoints

The percentage of patients with primary effectiveness success rates as defined in section 4 will be reported by randomized groups. The 95% confidence interval (CI) calculated using the Clopper-Pearson² exact method for binomial data will be reported by randomized groups. No formal statistical testing of the differences in primary effectiveness rates by randomized groups will be performed.

Similarly, the percentage of patients with MACE together with its 95% CI calculated using the Clopper-Pearson exact method will be reported by randomized groups. The number and percentage of patients in each of the MACE components will also be reported by randomized groups.

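### The plan compares observed with expected rates, but states no expected rate for the primary effectiveness composite by randomized group (its components imply about 72% to 75%) and does not settle whether that denominator or the 50 early-cannulated patients is primary.

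*Combined protocol and SAP*

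**What the plan says.** The study objective in Section 1.0 is to "demonstrate that early access of Artegraft is associated with acceptable rates of successful early access", together with acceptable rates of adverse events, in support of a labelling change. The primary effectiveness endpoint in Section 4.0 is a composite: "Early access success, defined by three cannulations, the first one started within 72 hours post implantation", with flow-rate and needle conditions.

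Section 4.0 attaches two expectations to it. About 80% "of patients in the early access group will have first cannulation within 72 hours", and about 90% "of patients receiving early access will have 3 successful cannulations". For safety it says: "Expectation: ~20% of patients will have at least one MACE event".

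On analysis, Section 9.2.2 says: "The percentage of patients with primary effectiveness success rates as defined in section 4 will be reported by randomized groups". It adds exact (Clopper-Pearson) 95% intervals for both primary endpoints. Section 9.1 calls the sample size logistical, promises confidence intervals for each endpoint, and ends: "The observed rates will be numerically compared with the expected rates and no formal statistical hypothesis will be tested". Section 9.2.6 says that all randomized patients are analyzed in their assigned group whatever access time they received.

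Other sections use a different denominator. Section 3.3 places patients cannulated within 72 hours in the primary analysis. The Data Populations entry of Section 1.0 defines the early-access group as the 50 patients who were cannulated in that window. Section 6.0 replaces patients who miss it until 50 is reached, and Section 6.8 estimates that there may be up to 10 of them.

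**The concern.** A comparison with an expected rate means something only if both rates share a denominator. Here the endpoint is a composite, the two expectations are for its parts, and the second is conditional on the first. The rate that a trial running exactly to plan would produce in the randomized group is not written down.

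The label *early access group* also carries two meanings. The 80% expectation makes sense only for patients randomized to early access. Under the Data Populations definition, 100% of the group is cannulated within 72 hours by construction. On that second definition, every failure of the 72-hour part is replaced and leaves the denominator.

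The figure presented as the primary result could therefore differ by 15 to 18 percentage points depending on a choice that the plan leaves open. A correct 72% could be set beside an 80% or 90% that was never meant for it. And because no acceptable success rate is defined, nothing says what the promised intervals are to be read against.

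**Working it through.** The plan has no power or sample-size calculation to reproduce.

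**Inputs.** 80% and 90% (Section 4.0); 50 patients cannulated within 72 hours (Section 9.1); up to 10 not cannulated in time (Section 6.8); expected MACE 20% (Section 4.0); exact 95% intervals (Section 9.2.2).

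**Step 1. Expected composite rate in the randomized group.** P(first cannulation in time) × P(three successful cannulations, given that) = 0.80 × 0.90 = 0.72.

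**Step 2. Number randomized to early access.** At 80%, 50 / 0.80 = 62.5, so 62 or 63 patients, of whom 12 or 13 miss the window. With 10 missing it, 60 are randomized, 50/60 = 83.3% are cannulated in time, and the composite is 0.833 × 0.90 = 0.75. The 80% and the estimate of up to 10 therefore do not agree. Fewer than 10 misses would raise the composite further.

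**Step 3. Planned result on each denominator.** Successes: 0.90 × 50 = 45.

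| Denominator | Observed | Exact 95% CI |
|---|---|---|
| All randomized to early access, 80% cannulated in time | 45/63 = 71.4% | 58.7% to 82.1% |
| All randomized to early access, 10 not cannulated in time | 45/60 = 75.0% | 62.1% to 85.3% |
| Only those cannulated in time | 45/50 = 90.0% | 78.2% to 96.7% |

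The same 45 successes give all three rows.

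**Step 4. How uninformative a bare point comparison is.** Suppose, for illustration only, that an observed rate on the wrong side of the expected value counted as a shortfall. With X binomial(n, p) and p equal to the expected rate, the chance of a shortfall for success is P(X < np), and for MACE it is P(X > np).

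| Endpoint | n | Shortfall if | Probability |
|---|---|---|---|
| Success, 90% (conditional) | 50 | fewer than 45 | 38.4% |
| MACE, 20% | 50 | more than 10 | 41.6% |
| Composite, 72% | 60 | fewer than 44 | 52.6% |
| Composite, 72% | 61 | fewer than 44 | 44.4% |
| Composite, 72% | 62 | fewer than 45 | 47.6% |
| Composite, 72% | 63 | fewer than 46 | 50.7% |

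**Step 5. The interval reading, for contrast.** If the true composite is 72%, the upper exact 95% limit falls below 72% in 1.6% of trials at n = 60, 2.4% at n = 62 and 1.6% at n = 63. Read this way, the data are seldom called inconsistent with an expectation that is true.

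**The case against.** The strongest reply has four parts.

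- **There is no decision rule.** A reader might infer from Section 9.1 that the trial is judged by whether the point estimate reaches the expected value, and so that about four in ten devices performing as expected would fail. The documents do not support this. Section 9.1 describes a numerical comparison, attaches no consequence to a shortfall, and promises intervals in the same paragraph. The expectations are marked as approximate. The Step 4 probabilities describe a strict cut that the plan does not contain. Four in ten also fits only n = 50; for the 72% composite at n = 60 to 63 the figure is 44% to 53%. This part of the reply stands in full.
- **An expected rate does exist.** On the 50 patients cannulated in time, 90% is the matching expectation, and Section 3.3 supports that denominator. So it would be wrong to say that the endpoint has no expected rate at all. But Sections 9.2.2 and 9.2.6 use randomized groups, so the reply shows that two denominators are live; it does not settle which is primary. The Data Populations entry is itself mixed, since it opens by putting all implanted patients into the performance analysis.
- **72% is not the only implied figure.** Correct: Section 6.8 supports about 75%. Neither figure is stated in the plan.
- **Descriptive analysis was deliberate.** Appendix 6 records that it was clarified at FDA request, and a formal performance goal is partly a design preference. That stands, but a descriptive comparison still needs matched denominators. The 20% MACE figure in Section 10.2.6 is a stopping rule. It does not define acceptable safety at the end of the trial, and it says nothing about success.

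**Conclusion.** The point holds as a gap in definition, with no arithmetic error in the plan. On the denominator in Section 9.2.2, the primary effectiveness composite has no stated expected rate. The plan's own components imply about 72%, or about 75% with 10 patients missing the window, against about 90% on the 50-patient denominator. The sections conflict on which denominator is primary, the 80% and the estimate of up to 10 disagree modestly (12 or 13 against 10), and no criterion is given for acceptable success although the objective is to demonstrate it.

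The figures assume that the 90% is conditional on cannulation within 72 hours, as its wording indicates, that patients who miss the window count as failures of the composite, and that exactly 50 are cannulated in time. A reader might also conclude that the sponsor would switch to the more favourable 90% after seeing the data. Nothing in the documents shows such an intention; they only leave both readings available. The plan should be changed on this point, but the defect does not invalidate the design.

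**What to change.** 1. Reconcile Section 3.3 and the Data Populations entry with Sections 9.2.2 and 9.2.6. Use all patients randomized to early access as the primary denominator, counting those not cannulated within 72 hours as not successful. Report the 50 cannulated patients as a labelled conditional analysis. State in Section 9.2.8 that patients who miss the window stay in the effectiveness population.
2. In Section 4.0 state the expected composite rate on that denominator: about 72%, or about 75% if the estimate of up to 10 stands. Choose between the two inputs. Keep 80% and 90% as components, each with its denominator.
3. In Section 9.1 say that the exact 95% intervals, not the point estimates, are read against the expected rates or against limits fixed before data are seen.
4. If no limits are set, change *demonstrate* to *estimate* in the objective.

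These are wording changes that add no patients, visits or data. The cost is a less favourable stated expectation (72% to 75% in place of 90%) and, under item 4, a more modest objective.
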